# 4.3 Secondary Outcomes

Secondary objectives of this study include determining whether nSTRIDE APS is superior to HA with regard to the endpoints in **Table 4**. These tests will be performed if the primary null hypotheses have been rejected. These secondary hypotheses will be tested using a fixed-sequence procedure, constructed using a pre-specified order of hypotheses. The order is shown in **Table 4**. These tests will be performed at the 0.05 level for each consecutive test until one hypothesis is tested not significantly, after which all subsequent tests will not be performed as secondary analyses, but instead will be performed as exploratory analyses only. Since the order of the tests is fixed a priori, and each subsequent hypothesis is tested only if the previous hypotheses have been rejected, the principle of closed testing implies that no adjustment to control the familywise error rate is necessary [11].

In particular, it is hypothesized that APS is superior to HA with regard to an improvement in both function and pain; thus these comprise the first two secondary endpoints tested. The subjects showing a minimum clinically important difference (MCID) in the WOMAC Function subscale will be referred to as "MCID Function responders." The proportion of subjects showing a MCID in the WOMAC Pain subscale (i.e. "MCID Pain responders") will be tested as the second-ranked secondary endpoint.

The development of the MCIDs for Function and Pain for which a patient is designated as a "function responder" or a "pain responder" is based on the data from the PROGRESS II pilot study. It is advantageous to use this data for the following reasons:

- The MCID is very much dependent on the choice of clinical score and the scale/version of the score and the follow up time point, so the best approach is to use pilot data where these variables are the same as in the current study.
- The Progress II data allows for development of an MCID that is context-specific, as it has the same or similar patient population, time point, baseline characteristics, and baseline symptom severity as this PROGRESS V study. These factors are important to consider in establishing an MCID [13].
- The Pilot study collected a transition question in which patients could rate their improvement as "Very Much Improved", "Improved", "Minimally Improved", "No Change", "Minimally Worse", "Much Worse",

and "Very Much Worse". This question can be used as external criteria to define patients who have experienced a meaningful change in their condition [14].

- Other potential anchor questions are also available in the Pilot study, serving as a way to verify the MCIDs and make sure that the MCIDs based on these different possible anchor questions are consistent.
- The change that a patient rates as "clinically significant" is dependent on the expectations of the patient [15]. This can vary by treatment as well as by time period.

The MCIDs were derived using an anchor-based method with the patient transition question described above. This question is an appropriate anchor as it is easily clinically interpretable, as well as correlated with the WOMAC Function and Pain scores as shown in the table below. In the Pilot study, the mean improvement in WOMAC Function and Pain scores increases with each increasing patient rating:

TRANSITION QUESTION	N	WOMAC ADL Mean Improvement from Baseline to 12 months	WOMAC Pain Mean Improvement from Baseline to 12 months
Very Much Worse	1	-7.0	-1.0
Much Worse	1	4.5	1.5
Minimally Worse	5	3.8	3.2
No Change	6	7.4	4.2
Minimally Improved	9	15.8	5.8
Much Improved	18	25.3	8.4
Very Much Improved	4	37.8	10.9

Thus the anchor is appropriate as described in methodology in Guyatt, et al.[16] and the MCID is calculated as follows:

The AAOS published a guideline in which calculations of minimum clinically important improvement (MCII) were presented [17]. These calculations of MCII were based on patients with knee osteoarthritis whose final outcome of treatment was "good, satisfactory effect with occasional episodes of pain or stiffness." The final response to treatment anchored by the baseline value was calculated for each patient. The determinations of clinical significance required patients in the included studies to achieve a change score comparable to that achieved by 75% of patients reporting good outcomes in the population.

In order to implement this method, the PGI-C response that most closely corresponds to a "good" result was determined. The closest category to the

AAOS definition was the "much improved" response (assuming that "minimally improved" corresponds to "fair", and "much improved" corresponds to "good"). The 25th percentile of the distribution of WOMAC Pain scores (improvement from baseline) for these subjects corresponds to a score achieved by 75% of the patients reporting a "much improved (= good)" outcome.

In order to verify the MCID, other anchor question alternatives corresponding to a "good" outcome were explored:

- The SF-36 health transition question, using subjects who respond with "somewhat better"
- The symptom to benefit ratio, which takes into account the symptoms described by the AAOS definition "occasional episodes of pain or stiffness". This includes subjects in the "Moderate/None" category.

The change from baseline in WOMAC function and pain scores for subjects within the appropriate category of each of the three measures were used to calculate and verify the MCID. The MCIDs (i.e. 25th percentile of the distribution of WOMAC Function and Pain Improvement scores) calculated using each of these three anchor questions are presented below.

Transition Question	MCID for Improvement in WOMAC Function from Baseline to 12 Months	MCID for Improvement in WOMAC Pain from Baseline to 12 Months
Based on 25 th percentile of the PGI = "Much Improved" subjects	20.0 points	7.0 points
Based on 25th percentile of the SF-36 health transition question	20.5 points	7.0 points
Based on 25th percentile of the symptom to benefit ratio = "Moderate/None"	16.5 points	7.0 points

The 25th percentiles for each of the three measures were remarkably similar to each other.

To further assess the validity of the MCIDs, the percentage of subjects in each transition category who met the MCID for Function and Pain were calculated, and are as follows:

TRANSITION QUESTION	PERCENT OF SUBJECTS MEETING WOMAC Function MCID	PERCENT OF SUBJECTS MEETING WOMAC Pain MCID
Very Much Worse	0%	0%
Much Worse	0%	0%
Minimally Worse	0%	0%
No Change	16.7%	50%
Minimally Improved	44.4%	55.6%
Much Improved	77.8%	83.3%
Very Much Improved	100%	100%

Based on this data, the MCID is an appropriate differentiator of subjects who are Much improved or Very Much Improved.

Therefore, the MCID Function responder criterion is as follows:

#### MCID Function Responder:

A subject is considered an MCID Function responder if they show an absolute improvement of  $\ge$  20.0 points in WOMAC Function from baseline to 12 months.

A two-tailed Fisher's Exact will be used to test the first secondary endpoint. The hypotheses will be:

H0: pAPS = pControl

Versus

HA: pAPS  $\neq$  pControl

Where:

pAPS = proportion of MCID function responders in the APS group, and

pcontrol = proportion of MCID function responders in the Control group

#### MCID Pain Responder.

A subject is considered an MCID Pain responder if they show an absolute improvement of  $\ge$  7.0 points in WOMAC Pain from baseline to 12 months.

A two-tailed Fisher's Exact will be used to test the first secondary endpoint. The hypotheses will be:

H0: pAPS = pControl

Versus

HA: pAPS  $\neq$  pControl

Where:

pAPS = proportion of MCID pain responders in the APS group, and

pcontrol = proportion of MCID pain responders in the Control group

The next sequential secondary endpoint will be a comparison of the mean change in WOMAC function score change from baseline to 12 months post-injection.

These analyses of WOMAC function and pain were chosen as the first, second, and third-ranked secondary endpoints for analysis because increased pain and decreased function are the predominant clinical findings associated with OA, making both pain and functional improvement important aspects in the treatment of OA. It is anticipated that if treatment with APS decreases pain, it may also increase function.

Following the test of the mean change from baseline in WOMAC function, the OMERACT-OARSI Responder Criteria [18] will be applied to both treatment groups, categorizing each patient into one of two categories: responder and non-responder. These results will be tested to determine whether a difference between treatment groups exists. With respect to the OMERACT-OARSI classification, all measurements where a pain measurement is called for will employ NRS pain. For evaluation of function in the OMERACT-OARSI classification, all measurements will be based on WOMAC function scores. For the global assessment variable, the EQ-5D global assessment VAS scale will be used for OMERACT-OARSI classification. For the function score, absolute change must equal 20% of the total possible score to meet the criteria of an absolute change  $\geq$  20, and 10% of the total possible score to meet the criteria of an absolute change  $\geq$  10.

Responders will be defined as subjects who achieved a high degree of improvement in pain or in function (improvement of  $\geq$  50% and absolute change  $\geq$  20), or a moderate degree of improvement in 2 of the 3 response domains (pain, function, global assessment) as follows (Figure 1):

(1) NRS pain improvement of  $\geq$  20% and absolute improvement of  $\geq$  1 point (2) WOMAC function improvement of  $\geq$  20% and absolute improvement of  $\geq$ 

8	Mean WOMAC Pain A (12 Month minus Baseline) with Usage of rescue medication within 48 hours of the 12 month visit for knee OA as a covariate	ANOVA	Exploratory

# Table 4 - Planned Secondary Efficacy Tests

Order of	Secondary	Test	Expected
Testing	Outcomes		Outcome
9	Mean WOMAC Pain A (12 Month minus Baseline) with Usage of rescue medication within 48 hours of the 12 month visit for any reason as a covariate	ANOVA	Exploratory
10	Mean WOMAC Pain A (12 Month minus Baseline) with Usage of restricted medication within 48 hours of the 12 month visit for knee OA as a covariate	ANOVA	Exploratory
11	Mean WOMAC Pain $\Delta$ (12 Month minus Baseline) with Usage of restricted medication within 48 hours of the 12 month visit for any reason as a covariate	ANOVA	Exploratory
12	Mean NRS Pain ∆ (12 Month minus Baseline)	T-Test or WMW	APS Superior
13	Mean WOMAC Pain changes over time within treatment	Repeated measures ANOVA	Significant change from baseline

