Secondary objectives of this study include determining whether nSTRIDE APS is superior to HA in improving WOMAC LK 3.1 function at 12 months (as evaluated using the percentage of subjects showing at least the minimal clinically important difference (MCID)), and WOMAC LK 3.1 pain at 12 months (as evaluated using the percentage of subjects showing at least the minimal clinically important difference (MCID)), OMERACT-OARSI responder rates at 12 months, analyzing WOMAC pain and function in only the KL-II Subgroup at 12 months, evaluating superiority of APS over HA in improving Numeric Rating Scale (NRS) pain at 12 months, assessment of the changes in WOMAC Pain scores over time (baseline through 12 months), and evaluation of the usage of rescue medication within 12 months. These will be tested in a fixed sequential order pending the rejection of the primary null hypothesis.

Exploratory objectives of this study include determining whether APS is superior to HA with regards to improvement in mean EQ-5D outcomes (12 months minus baseline) and repeated measures of WOMAC Function, WOMAC stiffness, and total WOMAC score. In addition, changes in joint morphology (determined with X-ray images) will be evaluated. Subgroup analyses will be conducted to investigate whether the treatment effect varies depending on subjects' initial pain and baseline information. Analysis of exploratory endpoints will be done using alpha=0.05 with no adjustment for multiple comparisons.

A long-term follow-up phase will examine the superiority of nSTRIDE APS in the duration of the treatment effect, injection frequency, patient preferences, healthcare resource utilization, and associated costs. These endpoints will be treated as exploratory endpoints and analyses will be conducted using alpha = 0.05 with no adjustment for multiple comparisons.

Finally, the safety profile of nSTRIDE APS will be compared to HA by comparing adverse events and rates between treatment groups.

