# 4.4 Exploratory Outcomes (Phase I)

#### 4.4.1 Questionnaire Data

Exploratory objectives of this study include determining whether nSTRIDE APS is superior to HA with regard to the endpoints in **Table 5**. Where repeated measures tests are statistically significant, tests at individual time

points will be performed. All tests will be conducted at  $\alpha$  = 0.05 and will not be adjusted for multiple comparisons as these are exploratory outcomes.

Exploratory Outcomes	Test	Expected Outcome
Mean NRS Pain Δ (1, 3, 6 Months)	Repeated Measures ANOVA	Trend APS Superior
Mean WOMAC Pain ∆ (Percent change from baseline to12 Month)	T-Test or WMW	APS Superior
Mean WOMAC Function Δ (Percent change from baseline to12 Month)	T-Test or WMW	APS Superior
Mean WOMAC Function changes over time within treatment	Repeated measures ANOVA	Significant change from baseline
Mean EQ-5D ∆ Global Assessment VAS (12 Month minus Baseline)	T-Test or WMW	APS Superior
Mean EQ-5D Δ Global Assessment VAS (Percent change from baseline to12 Month	T-Test or WMW	APS Superior
Mean EQ-5D Global Assessment VAS changes over time within treatment	Repeated measures ANOVA	Significant change from baseline
Mean EQ-5D *∆ Single Index Value (12 Month minus Baseline)	T-Test or WMW	APS Superior
Mean EQ-5D ∆ Single Index Value (Percent change from baseline to12 Month	T-Test or WMW	APS Superior
Mean EQ-5D Single Index Value changes over time within treatment	Repeated measures ANOVA	Significant change from baseline

 Table 5 – Planned Exploratory Analyses, Questionnaire Data

Exploratory Outcomes	Test	Expected Outcome
EQ-5D Dimensions (Mobility, Self-Care, Usual Activities, Pain/Discomfort, Anxiety/Depression) (12 Month)	Likelihood Ratio Chi-Square	APS Superior
Mean WOMAC Pain ∆ (1, 3, & 6 Months)	Repeated Measures ANOVA or Friedman Test	Trend APS Superior
Mean WOMAC Function Δ (1, 3, & 6 Months)	Repeated Measures ANOVA or Friedman Test	Trend APS Superior
MCID WOMAC Function Responder (1, 3, & 6 Months)	Fisher's Exact Family α = 0.05	Trend APS Superior
MCID WOMAC Pain Responder (1, 3, & 6 Months)	Fisher's Exact Family α = 0.05	Trend APS Superior
OMERACT-OARSI Responder / Non-responder** (1, 3, 6 & 12 Months) **Traditional published criteria; i.e. not including multiple restricted/ rescue medication usage between 6-12 months	Fisher's Exact Family α = 0.05	Trend APS Superior
Total Mean WOMAC Δ (1, 3, & 6 and 12 Months)	Repeated Measures ANOVA or Friedman Test	Trend APS Superior

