#### 6.1 Sample Size

Data used to estimate sample size are from Zimmer Biomet study APSS-33-00, a randomized study comparing APS to saline in human subjects. This calculation assumes that hyaluronic acid will perform similarly to saline. Estimates of expected difference and pooled standard deviation from this study are shown in **Table 15**.

Group	n	Mean Improvement in WOMAC	St. Dev.	Mean Diff.	Pooled St. Dev.	Sample Size Each	Combined Plus 20% Attrition
		Palli				Group	
APS	30	7.20	3.25				
Saline	15	4.93	4.73	2.27	4.06	93	246

Table 15- Results from APSS-33-00

The calculation results in 93 per group. Results are based on a two-tailed alpha of 0.049 and statistical power of 90%.

Planned enrollment was increased to 123 per group to protect against attrition of approximately 25% in either treatment group.

<sup>1 Under the original sample size calculations, the sample size of 196 randomized (98 per group) was adjusted to accommodate potential dropout rate of approximately 20%, resulting in a total sample size of 246. This sample size

A maximum of 30 sites will participate in the study. Enrollment will be stopped at any site reaching a limit of 30% of planned study enrollment.

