# 6.3.2 Sensitivity Analyses

Scores for subjects who are withdrawn due to reasons related to the index knee OA are considered Missing Not At Random. In all of the ITT analyses described below, these subjects will be considered "non-responders", and the subjects' baseline score will be used in the analysis of WOMAC Pain.

The primary study analysis assumes that the all other missing data is Missing At Random (MAR).

In order to investigate the assumption that the missing data (excluding the non-responders who are withdrawn for reasons related to the index knee OA)

<sup>2 If data are severely non-normal based on a graphical review, then the predictive mean matching method will be used instead of the monotone regression method.

is MAR, sensitivity analysis of the primary study endpoint will be performed under assumption of other missing data mechanisms, as follows:

- 1. A complete case analysis on the ITT population (Missing Completely at Random (MCAR))
- 2. A complete case analysis on the Per Protocol population (Missing Completely at Random (MCAR))
- 3. A tipping point analysis on the ITT population, performed under the assumption that the data is not MAR or MCAR by searching for a tipping point that reverses the study conclusion. This analysis will examine the possibility that the distribution of missing responses will have a different expected value than that of the corresponding distribution of the observed responses. Thus, the analysis will generate multiple imputed data sets with a specified sequence of shift parameters that adjust the imputed values for observations in the treatment group (Missing Not At Random (MNAR)).

In the event the conclusion from one or more of the sensitivity analyses disagrees with the conclusion from the primary analysis, the sources of differences between them will be investigated and subjected to explicit discussion and interpretation.

Prior results indicate that the efficacy of APS and the saline control differs over time, but this difference is small until some point after the 6 month postinjection time point. Therefore, although carrying data forward from an earlier time is commonly applied as a sensitivity analysis, in this case it is likely to produce misleading results if applied to primary endpoints and so is not planned.

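### Row 13 of SAP Table 4 tests pain change within each arm, so it gives no APS-versus-HA answer on pain over time

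*SAP*

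**What the plan says.** SAP section 4.3 opens with "Secondary objectives of this study include determining whether nSTRIDE APS is superior to HA with regard to the endpoints in" Table 4. The order is fixed: "These tests will be performed at the 0.05 level for each consecutive test until one hypothesis is tested not significantly". Everything after that point becomes exploratory.

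Most rows of Table 4 compare the arms. Row 13, the last, is "Mean WOMAC Pain changes over time within treatment", by repeated measures ANOVA, with expected outcome "Significant change from baseline". No treatment or treatment-by-visit term is named. The protocol synopsis lists WOMAC Pain over time among the secondary endpoints, and SAP section 1 places it among the objectives tested in sequence.

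Table 5 has exploratory rows of the same kind, such as "Mean WOMAC Function changes over time within treatment", and likewise for the EQ-5D VAS and index value.

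Two other places bear on the point. In the protocol synopsis, entry requires a WOMAC pain score of 9 to 19, and that screening score serves as the baseline without being repeated before injection. SAP section 6.3.2 says of APS and saline in prior results that "this difference is small until some point after the 6 month postinjection time point".

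**The concern.** A test of change from baseline inside one arm mixes any treatment effect with placebo response and regression to the mean. Both are likely here. Subjects are selected on a pain score of at least 9 on a 0 to 20 scale (5 items scored 0 to 4), and the selecting score is itself the baseline. A significant fall is therefore to be expected under either treatment.

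Two things are at stake. The protocol's secondary endpoint on pain over time gets a test that says nothing about APS against HA. And if the sequence does reach row 13, a result that was almost certain in advance would be listed with the confirmatory secondary findings of a comparative trial.

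**Working it through.** **Inputs.** The control row of SAP Table 15 reads "Saline 15 4.93 4.73 2.27 4.06 93 246": n, mean improvement, SD, mean difference, pooled SD, n per group, total. The APS row gives n = 30, mean 7.20, SD 3.25. Section 6.1 assumes HA behaves like saline, uses two-sided alpha 0.049 and 90% power, and plans 123 per group.

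**The plan's own figure.** n per group = 2(z₁ + z₂)²(SD/d)², with z₁ + z₂ = 1.969 + 1.282 = 3.250.
- SD 4.06, d 2.27: 2 × 10.56 × 3.199 = 67.6, so 68 (69 by the t distribution).
- SD 4.73, d 2.27: 2 × 10.56 × 4.342 = 91.7, so 92 (93 by the t distribution).

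The stated 93 matches the saline SD, not the pooled SD printed beside it. That is a separate matter. Here 93 serves only as the planned analysable number, with 123 as the other end of the range.

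**Within-arm test on the pilot arms.** The planned multi-visit ANOVA cannot be rebuilt, because visit means and correlations are not given. The stand-in is a one-sample t-test, t = mean/(SD/√n), equivalent to a within-arm ANOVA on two time points.
- Saline: 4.93/(4.73/√15) = 4.93/1.221 = 4.04, 14 df, p = 0.0012, 95% CI 2.31 to 7.55.
- APS: 7.20/(3.25/√30) = 12.13, p < 0.0001.

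**Between-arm test on the same data.** Pooling by degrees of freedom, SD = √[(29 × 3.25² + 14 × 4.73²)/43] = 3.80. Then t = 2.27/(3.80 × √(1/30 + 1/15)) = 1.89, p = 0.065 (Welch p = 0.11). Both arms pass the within-arm test, while the difference between them does not reach 0.05.

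**At the planned size, SD 4.73.**
- Smallest significant mean change: 1.986 × 4.73/√93 = 0.97 points; with 123 per arm, 0.84.
- A saline-like arm of 93: t = 4.93/(4.73/√93) = 10.05; power above 99.99%.
- If the true fall were only 2.0 points, power is 98.1%; at 1.5 points, 85.7%.
- If APS were worse than HA by 2.27 (true fall 4.93 − 2.27 = 2.66), its within-arm test still has 99.97% power.

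**Simulation** (20,000 runs, 93 per arm, SD 4.73, tests at 0.05):

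| Truth | APS within | HA within | Between arms |
|---|---|---|---|
| No difference | 100% | 100% | 5.0% |
| Difference 2.27 | 100% | 100% | 90.5% |

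**Supporting figure.** In the pilot transition table of section 4.3, which is labelled baseline to 12 months, patients reporting no change (n = 6) improved by 4.2 pain points on average, and those minimally worse (n = 5) by 3.2. These groups are small and the treatment arm is not given, but both means are well above 0.97.

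**The case against.** The best defence is that row 13 does not claim superiority. Its expected outcome is a change from baseline, sections 1 and 4.3 say only that the objectives include superiority, and rows 8 to 11 are labelled exploratory, so Table 4 already holds rows with other aims. This stands in part: the conflict is between the row and the sentence that introduces the table, and the row's own label is candid.

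The second defence is position, and it stands in full. Row 13 comes after the primary test and twelve other rows. If any of those fails, it is exploratory. A reader might infer that the plan could turn a meaningless within-arm result into a confirmatory success even if APS does not work. The sequence does not allow that unless the between-arm primary test and the earlier rows have all been rejected. Nor does row 13 inflate the familywise error or touch the primary test, since nothing follows it.

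Third, a reader might infer that the plan has no between-arm analysis of pain at the other visits. It has: the primary test at 12 months and, as exploratory, a repeated measures analysis at months 1, 3 and 6 in Table 5. What is missing is one between-arm model of WOMAC Pain spanning months 1 to 12. Table 5 has such a row for total WOMAC and for stiffness. The within-treatment rows of Table 5 matter less, because they are exploratory and have between-arm companions.

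Last, the t-tests are proxies. Table 15 does not label its time point, saline stands in for HA, and the per-protocol number used for secondary endpoints is not known. These limits affect the exact p-values. They do not affect the fact that a within-arm test makes no comparison.

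**Conclusion.** The point holds, with a limited consequence. Row 13 cannot inform the APS-versus-HA question that section 4.3 sets for Table 4, and it leaves the protocol's secondary endpoint on pain over time without a comparative answer.

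If HA performs like saline, the SD is near 4.73 and about 93 to 123 per arm are analysed, the test is near certain to be positive in both arms. It would become uncertain only if the true within-arm fall were much smaller than any the pilot suggests, around 1.5 points or less. It should not be said that the pilot saline arm passed the planned test: that test was not run on those data, and the one-sample result assumes that the Table 15 figure is the 12-month change.

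The primary conclusion and error control are untouched. This is worth correcting because the row adds nothing comparative where it stands and a useful analysis could take its place.

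**What to change.** Replace row 13 with a between-arm repeated-measures model of WOMAC Pain change at months 1, 3, 6 and 12, with treatment, visit, treatment-by-visit and baseline pain. Name one APS-minus-HA contrast in advance as the single p-value, for example the average difference over the four visits, and give each visit's difference with a 95% CI.

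The treatment-by-visit interaction should not be that p-value on its own. It asks whether the difference changes between visits, so it would miss a constant APS benefit, and it has no direction.

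The average has a downside, given the late separation that section 6.3.2 expects. In the extreme case of no difference at months 1, 3 and 6 and 2.27 at month 12, the average is 2.27/4 = 0.57. Because row 13 is last, that loss of power affects no other test, and the per-visit differences would show the pattern.

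Report within-arm changes descriptively, here and in the within-treatment rows of Table 5. If the sponsor wants only a description of pain over time, take row 13 out of the tested sequence and say so in section 4.3.

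The cost is SAP wording and one model on data already collected.
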